Effect of number of remote limb ischemic conditioning cycles of learning enhancement.

NCT03512041

NIHR01HD085930-Aim2

05/19/2017

Effect of number of remote limb ischemic conditioning cycles of learning enhancement.

Study Objectives	
The objective of this research study is to determine if remote limb ischemic conditioning (RLIC) can serve as an agent to enhance motor and cognitive learning. The immediate goal is to test the effect of number of RLIC cycles on motor learning in neurologically intact adults. An additional goal is to determine a physiological marker of the effectiveness of RLIC through collecting blood samples during various time points throughout the study. The long term goal is to determine if RLIC, when compared to sham treatment, augments the learning that occurs during a rehabilitation training exercise in people who have motor deficits following stroke.

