
	
function in people with stroke. It is important to first start this translational investigation in neurologically intact people in order to determine optimal protocols for people with stroke.
 
The purpose of this study is to test the effect of number of RLIC cycles on motor learning in neurologically intact adults and if we can find a physiological blood marker related to effective administration of RLIC. We hypothesize that 3 cycles of RLIC will be sufficient to enhance motor learning compared to sham conditioning, and that there will be a dose-dependent (number of cycles) response in learning, thus making training more efficient, more effective, and longer-lasting. Determining the number of cycles necessary to elicit the benefits of RLIC is important in developing the most effective and least burdensome treatment for future patients with motor deficits.
																
Study Design	
Between subjects repeated measures design. Please refer to Figure 1.
																
Groups	
Group 1: Neurologically Intact Subjects + 5 cycles of RLIC Group 2: Neurologically Intact Subjects + 4 cycles of RLIC Group 3: Neurologically Intact Subjects + 3 cycles of RLIC Group 4: Neurologically Intact Subjects + 5 cycles of sham conditioning
 
Subjects who qualify and consent will be randomly assigned to either group 1, 2, 3 or 4. Allocation will be concealed from those responsible for assessing patients for eligibility and entry into the study.
																

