Number of Subjects & Power Analysis	
Based off of pilot data on the balance training task, we need the following total sample sizes moving forward (see Table 1 below) to achieve at least 80% power to detect the mean differences of change scores (posttest – pretest) between the two treatment groups (RLIC vs. sham) based on a two-sample t-test at a significance level of 0.05. The standard deviations for change scores are assumed to be 2.5 seconds and 1.9 seconds for the RLIC and sham groups, respectively. 10 subjects will be enrolled for each of the 4 groups. However, we request permission to enroll 55 subjects total to allow for screen failures and participants who do not complete all study visits. This will give us the ability to detect differences on the balance task of at least 3-4 seconds. Differences less than this (and smaller effect sizes) are unlikely to be clinically-relevant in future target populations.
 
Table 1. Power analysis
 
  
 Mean difference of change score	Total sample size (assume equal sample size in each group)	
   
 7 seconds	12 (with actual power 93%)	
 
 6	12 (with actual power 85%)	
 
 5	15	
 
 4	21	
 
 3	30	
 
 2	63	
 
 1	237 study visits.	
  
	Mean difference of change score	Total sample size (assume equal sample size in each group)	7 seconds	12 (with actual power 93%)	6	12 (with actual power 85%)	5	15	4	21	3	30	2	63	1	237 study visits.
Mean difference of change score	Total sample size (assume equal sample size in each group)																
7 seconds	12 (with actual power 93%)																
6	12 (with actual power 85%)																
5	15																
4	21																
3	30																
2	63																
1	237 study visits.																
Inclusion & Exclusion Criteria	
Inclusion Criteria: ¶ 1)Between the age of 18 and 40 years ¶ ¶ Exclusion Criteria: ¶ 1)History of neurological condition (i.e. stroke, Alzheimer's disease, Parkinson's disease), ADD, ADHD, balance impairment, or vestibular disorder ¶ 2)History of sleep apnea ¶ 3)History of lower extremity condition, injury, or surgery which could compromise performance on motor training task ¶
																

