Primary Outcome Measures	
The primary outcome measures are:
 
 1) Performance on the standing balance motor task 2) Performance on the arm task 3) Performance on the computer task 
Performance on the standing balance task will be quantified by the identifying the number of seconds in a 30-second trial that an individual is able to maintain the platform within $\pm 3^\circ$ of horizontal. Performance on the arm task will be measured by the time to complete the three cup-stacking structures. The measure of performance on the computer task will be the average time to complete each unique sequence in milliseconds.
 
Please refer to Table 1 for a summary of the assessment schedule.

Secondary Outcome Measure	
The secondary outcome measure is:
 
 1) Blood draw: probe for levels of serum markers of RLIC 
The blood draw will be performed by trained members of the Washington University Clinical Research Unit. Blood will be processed the Washington University CORE Laboratory. Please refer to Table 1 for a summary of the assessment schedule.

Data Analysis	Data will be analyzed using a mixed model ANOVA with a within subject factor of time (pretest vs. posttest) and a between subjects factor of conditioning (RLIC vs. sham treatment).
Safety Considerations & Monitoring	The study will be submitted to and approved by the Washington University Human Research Protection Office prior to initiation. The risks of participating in the rehabilitation

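### The planned ANOVA compares RLIC with sham as two groups, so it tests neither the 3-cycle hypothesis nor the dose-response hypothesis

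*Combined protocol and SAP*

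**What the plan says.** - **Study Objectives:** "The immediate goal is to test the effect of number of RLIC cycles on motor learning in neurologically intact adults".
- **Background Rationale**, closing paragraph, gives two hypotheses: "We hypothesize that 3 cycles of RLIC will be sufficient to enhance motor learning compared to sham conditioning", and "there will be a dose-dependent (number of cycles) response in learning".
- **Groups:** the arms are 5, 4 and 3 cycles of RLIC and 5 cycles of sham. "Subjects who qualify and consent will be randomly assigned to either group 1, 2, 3 or 4".
- **Number of Subjects & Power Analysis:** 10 participants per group, with change-score SDs of 2.5 s (RLIC) and 1.9 s (sham). The aim is "to achieve at least 80% power to detect the mean differences of change scores" between two treatment groups, RLIC and sham, "based on a two-sample t-test at a significance level of 0.05". The section says differences of at least 3 to 4 s on the balance task can be detected.
- **Data Analysis**, in full, is a "mixed model ANOVA with a within subject factor of time (pretest vs. posttest") and a "between subjects factor of conditioning (RLIC vs. sham treatment").

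No other section gives a four-level group factor, a number-of-cycles term, a trend test, a 3-cycles-against-sham contrast, a post hoc test or a multiplicity rule.

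**The concern.** With two levels of conditioning and two of time, the interaction has one degree of freedom. It asks whether RLIC averaged over dose differs from sham, and no term separates 3, 4 and 5 cycles.

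Two errors of interpretation follow. A significant pooled result could be taken as support for 3 cycles being enough when the effect came only from the higher doses. Conversely, a real effect confined to one or two doses can be averaged away and missed. Any dose comparison chosen after the data are seen would be unplanned, although it is the question the trial was randomised to answer.

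**Working it through.** **Inputs.** From the power section: n = 10 per group, SD 2.5 s (RLIC) and 1.9 s (sham), alpha 0.05. Assumed: two-sided testing, SD 2.5 s in each RLIC arm, normal change scores, and the true gains tabulated below. With two time points, the time-by-conditioning interaction is the equal-variance two-sample t-test on change scores.

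**Step 1. Reproduce the plan's figure.** One arm against sham, 10 against 10:

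- SE = √(6.25/10 + 3.61/10) = √0.986 = 0.993 s.
- With Satterthwaite degrees of freedom, power at a 3 s difference is 81% (Welch simulation 80.9%). The smallest difference with 80% power is 2.95 s.

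The stated 3 to 4 s therefore reproduces for a single RLIC arm against sham.

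**Step 2. What the written model estimates.** With equal arms, the pooled contrast is (δ3 + δ4 + δ5)/3, where δk is the gain over sham with k cycles. Opposite dose patterns give the same value: (0 + 3 + 6)/3 = (6 + 3 + 0)/3 = 3 s.

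**Step 3. Rejection rates** (simulation, 20,000 to 40,000 trials per scenario):

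| True gain at 3/4/5 cycles (s) | Average (s) | Pooled test as written | 3 cycles vs sham | Dose-sensitive test |
|---|---|---|---|---|
| 0/4/6 | 3.33 | 88% | 5% (no true effect) | not tabulated |
| 0/3/6 | 3 | 78% | 5% (no true effect) | linear trend 99.9% |
| 6/3/0 | 3 | 79% | 100% | linear trend 99.9% |
| 0/2/4 | 2 | 48% | 5% (no true effect) | four-group F 95%; 5 vs 3 cycles 92–93% |
| 0/0/3 | 1 | 11% | 5% (no true effect) | four-group F 79% |
| 3/3/3 | 3 | 95% | 81% | linear trend 5% (no true trend) |

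The 92–93% uses error from the RLIC arms only. With the four-group error term it is 95%. With three equal, equally spaced arms, the linear trend has weights −1, 0, 1 and is the same contrast as 5 against 3 cycles.

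The pooled test rejects almost equally often for 0/3/6 and 6/3/0, so it cannot tell a rising dose response from a falling one.

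**Step 4. Error term of the pooled test** (30 against 10):

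- SE used by the ANOVA = √{[(29×6.25 + 9×3.61)/38] × (1/30 + 1/10)} = √(5.625 × 0.1333) = 0.866 s.
- True SE = √(6.25/30 + 3.61/10) = √0.569 = 0.755 s.
- Ratio 0.866/0.755 = 1.15, so the SE is about 15% too large. Type I error is about 2.5% instead of 5%.

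**Step 5. Precision of the contrasts that answer the hypotheses** (80% power, alpha 0.05):

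- 3 cycles against sham: 2.95 s.
- 5 against 3 cycles, those two arms only: 3.31 s.
- Linear trend over 3, 4 and 5 cycles: slope SE = 2.5/√20 = 0.559 s per cycle. About 1.63 s per cycle is needed, or 2 × 1.63 = 3.26 s between 3 and 5 cycles.
- Pooled RLIC against sham: 2.22 s with unequal variances, about 2.4 s with the equal-variance test the ANOVA implies.

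**The case against.** The best defence is that RLIC against sham is shorthand. The protocol never says in words that the three RLIC arms are combined. The RLIC Treatment Parameters section also describes group assignment as RLIC or sham, although assignment is to one of four groups. And 10 per group fits one arm against sham (Step 1), which suggests that arm-level comparisons were in mind.

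This does not rescue the text. The power section independently describes two treatment groups and a two-sample t-test, so the two-group framing appears in both statistical sections. Even if a four-level factor was meant, its three-degree-of-freedom test would not by itself test 3 cycles against sham or a trend. Both would still have to be named.

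Four smaller points stand in part:

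- Most of the scenarios give 3 cycles no effect, contrary to the protocol's hypothesis. If all doses work equally (3/3/3 s), the pooled test is the strongest, at 95% against 81%. With gains of 3/4/5 s, which fit both hypotheses, it has over 99% power, while 5 against 3 cycles has only 39 to 46%. The planned test is not always weak; it answers a different question.
- The error-term distortion is conservative under the null. It rests on balance-task SDs, for one of three primary outcomes, and is secondary.
- That a pooled result would be misread is a risk, not something the protocol states.
- Added contrasts need a multiplicity rule, which has a price (see the fix).

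**Conclusion.** The concern holds and must be fixed. As written, the only specified analysis cannot answer the question in the trial's title or test either hypothesis. This follows from the structure of the model and depends on no assumed effect size.

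The numbers show how far the pooled answer can mislead: 88% rejection with no 3-cycle effect, and power of 48% against 95%, or 11% against 79%, when the effect is graded or confined to 5 cycles. They are conditional on the assumed gains, the plan's balance-task SDs, SD 2.5 s in every RLIC arm, and 10 completers per group. The randomised design is sound for this purpose; the fault is in the analysis text.

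**What to change.** In Data Analysis, replace the two-level conditioning factor with a four-level group factor (sham, 3, 4, 5 cycles), as randomised. Pre-specify two contrasts on the group-by-time interaction:

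1. 3 cycles against sham.
2. A linear trend across the 3, 4 and 5 cycle groups.

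Allow group-specific residual variances, keep pooled RLIC against sham as a secondary contrast, and state how multiplicity is handled across the two contrasts and the three primary outcomes. Bring the two-group wording of the power section into line.

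This is a text change with no new participants or data. The cost is precision. At 10 per group, 3 cycles against sham has 81% power at 3 s unadjusted. This falls to about 70% if alpha is split equally over the two contrasts, and to 64% if three dose-against-sham comparisons were Bonferroni-adjusted instead. The trend needs about 1.63 s per cycle for 80% power even before adjustment. The protocol should state these limits, so that a non-significant trend is not read as evidence that the number of cycles does not matter.
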